### 6.2 Antitumor Effect - Hematologic Tumors

Not applicable for this study.

### **6.3 Safety/tolerability**

Not applicable for this study.

## **7.0 ADVERSE EVENTS**

### **7.1 Experimental Therapy**

Not applicable

### **7.2 Adverse Event Monitoring**

Adverse event data collection and reporting, which are required as part of every clinical trial, are done to ensure the safety of subjects enrolled in the studies as well as those who will enroll in future studies using similar agents. Adverse events are reported in a routine manner at scheduled times during a trial. Additionally, certain adverse events must be reported in an expedited manner to allow for optimal monitoring of subject safety and care.

All subjects experiencing an adverse event, regardless of its relationship to study therapy, will be monitored until:

- the adverse event resolves or the symptoms or signs that constitute the adverse event return to baseline;
- any abnormal laboratory values have returned to baseline;
- there is a satisfactory explanation other than the study therapy for the changes observed; or
- death.

**[Inserted from Adverse Event Definitions and Reporting Section – Appendix IB SCCC DSMC Plan]**

#### **7.2.1 Definition**

Adverse Events will be reported as indicated by the appropriate following table (see below).

An adverse event is defined as any untoward or unfavorable medical occurrence in a human research study participant, including any abnormal sign (for example, abnormal physical exam or laboratory finding), symptom, clinical event, or disease, temporarily associated with the subject's participation in the research, whether or not it is considered related to the subject's participation in the research.

Adverse events encompass clinical, physical and psychological harms. Adverse events occur most commonly in the context of biomedical research, although on occasion, they can occur in the context of social and behavioral research. Adverse events may be expected or unexpected.

#### Severity

Adverse events will be graded by a numerical score according to the defined NCI Common Terminology Criteria for Adverse Events (NCI CTCAE) and version number specified in the protocol. Adverse events not specifically defined in the NCI CTCAE will be scored on the Adverse Event log according to the general guidelines provided by the NCI CTCAE and as outlined below.

- Grade 1: Mild

- Grade 2: Moderate
- Grade 3: Severe or medically significant but not immediately life threatening
- Grade 4: Life threatening consequences
- Grade 5: Death related to the adverse event

### Serious Adverse Events

ICH Guideline E2A and the UTSW IRB define serious adverse events as those events, occurring at any dose, which meets any of the following criteria:

- Results in death
- Immediately life-threatening
- Results in inpatient hospitalization or prolongation of existing hospitalization
- Results in persistent or significant disability/incapacity
- Results in a congenital anomaly/birth defect
- Based upon appropriate medical judgment, may jeopardize the subject's health and may require medical or surgical intervention to prevent one of the other outcomes listed in this definition.

Note: A “Serious adverse event” is by definition an event that meets **any** of the above criteria. Serious adverse events may or may not be related to the research project. A serious adverse event determination does not require the event to be related to the research. That is, both events completely unrelated to the condition under study and events that are expected in the context of the condition under study may be serious adverse events, independent of relatedness to the study itself. As examples, a car accident requiring overnight hospitalization would be a serious adverse event for any research participant; likewise, in a study investigating end-stage cancer care, any hospitalization or death which occurs during the protocol-specified period of monitoring for adverse and serious adverse events would be a serious adverse event, even if the event observed is a primary clinical endpoint of the study.

#### **7.2.2 Unanticipated Problems Involving Risks to Subjects or Others (UPIRSOs):**

The term “unanticipated problem” is found, but not defined in the regulations for the Protection of Human Subjects at 45 CFR 46, and the FDA regulations at 21 CFR 56. Guidance from the regulatory agencies considers unanticipated problems to include any incident, experience, or outcome that meets **each** of the following criteria:

- Unexpected (in terms of nature, severity or frequency) **AND**
- Definitely or probably related to participation in the research **AND**
- Serious or a possible unexpected problem in that the research places subjects or others at greater risk of harm than was previously known or recognized. Note: Any serious adverse event would always suggest a greater risk of harm.

#### Follow-up

All adverse events will be followed up according to good medical practices.

#### **7.2.3 Reporting**

The UTSW IRB requires reporting of all UPIRSOs according to the guidance below. For participating centers other than UTSW, local IRB guidance should be followed for local reporting of serious adverse events. All SAEs occurring during the protocol-specified monitoring period should be submitted to the UTSW study team within 2 business days of the center learning of the event.

**7.2.3.1** UPIRSOs occurring on the study require expedited reporting, and are submitted to the UTSW IRB through the UTSW eIRB by the UTSW study team and to the SCCC DSMC Coordinator. Hardcopies or electronic versions of the eIRB report; FDA Form #3500A forms, or other sponsor forms, if applicable; and/or any other supporting documentation available should be submitted to the UTSW study team and will be forwarded to the DSMC Coordinator. The DSMC Coordinator forwards the information onto the DSMC Chairman who determines if immediate action is required. Follow-up eIRB reports, and all subsequent SAE documentation that is available are also submitted to the DSMC Chair who determines if further action is required. (See *Appendix IV of the SCCC DSMC Plan for a template Serious Adverse Event Form which may be utilized when a sponsor form is unavailable and SAE submission to the eIRB is not required*).

All serious adverse events which occur on research subjects on protocols for which the SCCC is the DSMC of record require reporting to the DSMC regardless of whether IRB reporting is required. Hardcopies or electronic versions of the FDA Form #3500A forms, or other sponsor forms, if applicable; and/or any other supporting documentation available should be forwarded to the DSMC Coordinator.

If the event occurs on a multi-institutional clinical trial coordinated by the UTSW Simmons Cancer Center, the DOT Manager or lead coordinator ensures that all participating sites are notified of the event and resulting action, according to FDA guidance for expedited reporting. DSMC Chairperson reviews all serious adverse events upon receipt from the DSMC Coordinator. The DSMC Chairperson determines whether action is required and either takes action immediately, convenes a special DSMC session (physical or electronic), or defers the action until a regularly scheduled DSMC meeting.

Telephone reports to:            [name]            [contact]

---

## 1. SAEs

Serious adverse events (SAEs) for studies where the SCCC DSMC is the DSMC of record require reporting to the DSMC coordinator within 2 working days of PI awareness,

or as described in the protocol.

## 2. Unanticipated Problems Involving Risks to Subjects or Others (UPIRSOs)

Local Serious Adverse Event UPIRSOs require reporting to the UTSW IRB within 48 hours of PI awareness of the event (life threatening or fatal events experienced by subjects enrolled by the investigator(s) under UTSW IRB jurisdiction).

Local UPIRSOs (non-serious events experienced by subjects enrolled by the investigator(s) under UTSW IRB jurisdiction) require reporting to the UTSW IRB within 5 business days of PI awareness of the event.

External UPIRSOs including those that occur as non-local events require reporting to the UTSW IRB within 10 working days of PI awareness of the event.

For further guidance for Investigators regarding safety reporting requirements for INDs and BA/BE studies, refer to FDA Draft Guidance document:

<http://www.fda.gov/downloads/Drugs/GuidanceComplianceRegulatoryInformation/Guidances/UCM227351.pdf>

## 7.3 Steps to Determine If an Adverse Event Requires Expedited Reporting

Step 1: Identify the type of adverse event using the NCI Common Terminology Criteria for Adverse Events (CTCAE v4).

Step 2: Grade the adverse event using the NCI CTCAE v4.

Step 3: Determine whether the adverse event is related to the protocol therapy Attribution categories are as follows:

- Definite – The AE is *clearly related* to the study treatment.
- Probable – The AE is *likely related* to the study treatment.
- Possible – The AE *may be related* to the study treatment.
- Unrelated – The AE is *clearly NOT related* to the study treatment.

Note: This includes all events that occur within 30 days of the last dose of protocol treatment. Any event that occurs more than 30 days after the last dose of treatment and is attributed (possibly, probably, or definitely) to the agent(s) must also be reported accordingly.

Step 4: Determine the prior experience of the adverse event.

Expected events are those that have been previously identified as resulting from administration of the agent. An adverse event is considered unexpected, for expedited reporting purposes only, when either the type of event or the severity of the event is not listed in:

- the current known adverse events listed in the Agent Information Section of this protocol;
- the drug package insert;
- the current Investigator's Brochure

## 7.4 Unblinding Procedures

Patient information is not blinded and all information obtained from the imaging studies performed for the purposes of the study will be available to all clinics treating the patient.

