## STUDY SUMMARY

Title	A Prospective Study to Evaluate Quantitative Non-Contrast Perfusion using Arterial Spin Labeled MR Imaging for Assessment of Therapy Response in Metastatic Renal Cell Carcinoma
Short Title	Quantitative MRI for therapy response assessment in metastatic RCC
Protocol Number	STU 032018-078
Phase	N/A
Methodology	Prospective study to evaluate quantitative MRI metrics for the assessment of treatment response
Study Duration	48 months
Study Center(s)	Single-center
Objectives	To prospectively determine whether ASL-measured perfusion can identify treatment response earlier than the currently used RECIST criteria.
Number of Subjects	90 (40 subjects with RCC and 50 healthy volunteers)
Diagnosis and Main Inclusion Criteria	Diagnosis: Locally advanced or metastatic renal cell carcinoma Main Inclusion Criteria: Patients with histologically proven clear cell RCC, scheduled to undergo anti-angiogenic treatment or immunotherapy (IO) who are 18 years of age and older and have no contraindication to MRI.
Study Product(s), Dose, Route, Regimen	N/A
Duration of administration	N/A
Reference therapy	N/A
Statistical Methodology	Primary end points for this study will include the absolute days of time to disease progression, progression free survival (PFS) and overall survival (OS) as well as disease status (progression versus not) at 7 months post treatment initiation. Progression will be determined according to the clinical RECIST criteria. One-sample correlation test will be used to determine the correlation between change in ASL measured tumor perfusion during and immediately after treatment and time to progression, and the correlation between change in ASL measured tumor perfusion and the corresponding tumor size change. The correlations will be measured and compared using Pearson's correlation coefficient along with 95% confidence interval. PFS and OS will be correlated with baseline perfusion and post-treatment changes at T1, T2 and T3 compared to baseline using univariable and multivariable Cox regression models. Univariable and multivariable logistic regression models will be used to predict responders from non-responders (progression versus not at 7 months) with ASL measurements at baseline and at earlier time points (T1 and T2) alone, and in combination with other MR imaging metrics.

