#### **2.4 Endpoints**

Primary end points for this study will include the absolute days of progression free survival (PFS) and overall survival (OS). Additionally disease status (progression versus not) at 7 months and survival (dead or alive) at 24 months post-treatment initiation will also be documented. Progression will be determined based on the clinically accepted RECIST criteria.

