#### 5.4 Time and Events Table

##### RCC Subjects

	Pre-study	Week 0 (T0) before initiation of anti-angiogenic therapy	Day 7±2 (T1)	Day 14±2 (T2)	T3	T4	T5	Follow-up (As indicated by clinical protocol)
Assessment	X							
Informed Consent	X							
History and PE	X							
Tumor Measurements	X							
MRI*		X	X	X	X	X	X	X

\*Clinically, metastatic RCC patients are imaged every 2-3 months after the initiation of anti-angiogenic therapy, since morphological (i.e. size) changes are not anticipated earlier. However, our preliminary experience has shown functional changes including perfusion as early as 2-weeks after the initiation of the treatment (19). T0, T1, and T2 sessions will be performed for this proposal, while T3, T4, and T5 will be performed along with the clinical imaging sessions. The research MR imaging may take approximately an additional 15 minutes per each imaging session, when done in conjunction with the clinical imaging. The T0, T1, and T2 research MR imaging sessions will be performed additionally for the purpose of this study, with each taking approximately one hour.

The ASL portion of the study does not require contrast. Clinically, the subjects will also receive gadolinium based contrast injection for the MRI study to measure the blood flow to the tumors. This is done at the clinical imaging time points of T3, T4, and T5. Similar to this, the contrast agent will also be administered during the research portion of the study at T0, T1 and T2 time points, to compare the blood flow measured with ASL-MRI.

MRI including ASL will be performed before, during and after the treatment, in a total of 6 MRI sessions until 7 months after the first session, or when progression is clinically indicated. Thereafter, patients will be followed through standard clinical examinations for the next 3 years or until demise, whichever occurs first.

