## 6.0 Measurement of Effect

### 6.1 Antitumor Effect- Solid Tumors

This study is designed to monitor therapy response in metastatic RCC using MRI with both conventional methods and ASL. Hence, the standard clinical assessment will be performed using RECIST criteria with conventional MRI. The ASL defined therapy response is currently developmental and not yet defined. Based on prior studies, a coefficient of variance (COV) of 7% was observed in ASL measured perfusion within the same subject imaged at two different time points (21). Thus, we will use a threshold of >10% difference in ASL measured perfusion compared to baseline to define ASL measured therapy response.

Response and progression will be evaluated in this study using the new international criteria proposed by the Response Evaluation Criteria in Solid Tumors (RECIST) Committee [JNCI 92(3):205-216, 2000]. Changes in only the largest diameter (unidimensional measurement) of the tumor lesions are used in the RECIST v1.1 criteria.

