**10.3 Data Analyses Plans**

The perfusion difference images and the absolute quantified images will be converted to DICOM and transferred to a DICOM database (e.g. iPACS, OsiriX). A semi-automated segmentation algorithm and region of interest (ROI) based measures will be performed to extract perfusion measures. Percentage changes in perfusion within each ROI will be calculated at each follow-up MRI compared to the baseline image. The semi-automated tumor ROIs will be compared to expert segmentation by [name] in all cases, who will also supervise the trainee (to be recruited) in the analysis. Additionally, morphological changes will also be calculated according to RECIST and 10% reduction in the sum of the largest diameters (20).

Among patients with disease progression, one-sample correlation test will be used to determine the correlation between change in ASL measured tumor perfusion during and immediately after treatment and time to progression, and the correlation between change in ASL measured tumor perfusion during and immediately after treatment and the corresponding tumor size change. The correlations will be measured and compared using Pearson's correlation coefficient along with 95% confidence interval. PFS and OS will be correlated with baseline perfusion and post-treatment changes at T1 and T2

compared to baseline using univariable and multivariable Cox regression models. We used PFS at 7 months as a cutoff point to divide patients into “responders” versus “non-responders” in this study. Univariable and multivariable logistic regression models will be used to predict responders from non-responders with ASL measurements at baseline and at earlier time points (T1 and T2) alone, and in combination with other MR imaging metrics. The statistical analysis will also be performed separately for male and female subjects to evaluate sex as a biological variable.

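### The RECIST reading that supplies progression is not kept blind to the research ASL results, nor the ASL region-of-interest work blind to outcome

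*Combined protocol and SAP*

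**What the plan says.** Section 7.4 rules out any blinding and adds an affirmative rule on disclosure: "all information obtained from the imaging studies performed for the purposes of the study will be available to all clinics treating the patient". It sets no delay and does not separate ASL from conventional images.

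The endpoint comes from clinical care. Section 2.4 says "Progression will be determined based on the clinically accepted RECIST criteria", the Study Summary says "Progression will be determined according to the clinical RECIST criteria", and section 6.1 says "the standard clinical assessment will be performed using RECIST criteria with conventional MRI". The reader is not named.

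On timing, the Study Schema and section 5.4 place T1 at day 7±2 and T2 at day 14±2. Clinical imaging follows every 2 to 3 months, and "T3, T4, and T5 will be performed along with the clinical imaging sessions". Section 4.4 leaves treatment to the referring physician.

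On ASL itself, section 6.1 says "The ASL defined therapy response is currently developmental and not yet defined" and then adopts a working threshold of more than 10% change from baseline. In section 10.3 the only check on the segmentation is agreement: "The semi-automated tumor ROIs will be compared to expert segmentation by" an expert. Nothing is said about whether the expert or the trainee knows the patient's outcome.

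**The concern.** The primary aim (sections 2.1 and 10.1) is to show that early perfusion change tracks time to progression ahead of size change. That needs the two measurements to be made independently. Here the early ASL result exists before the scans that establish progression, and it is open to those treating the patient.

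Three routes follow:

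- **Reading.** RECIST leaves room for judgement in the choice of target lesions (6.1.1), unequivocal non-target progression (6.1.3.2) and new lesions. From T3 on, perfusion data are acquired in the same sessions as the clinical images.
- **Timing.** A poor perfusion result could bring forward the scan, or the date, on which progression is declared.
- **Treatment.** The referring physician could change management after seeing the result, which would also reach overall survival.

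In the other direction, someone who draws ASL regions knowing that the patient has progressed could place them differently.

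If a correlation is then found, the planned analysis cannot tell whether ASL anticipated progression or influenced when it was recorded.

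**Working it through.** **1. The plan's own figure.** Section 10.2 claims more than 95% power for a correlation of 0.75 with about 20 progressors, two-sided 0.05. By Fisher's z:

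- atanh(0.75) × √(20 − 3) = 0.973 × 4.123 = 4.01
- power = Φ(4.01 − 1.96) = Φ(2.05) ≈ 98.0%

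Simulating the Pearson t-test gives 98.3%. The stated power reproduces, and this point does not alter it. The issue is bias.

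**2. Search for a safeguard.** None of these appears in the document: a RECIST reader without access to ASL, independent or central review, a delay before ASL release, outcome-blind segmentation, a record of whether ASL was acted on, or a sensitivity analysis for treatment change. Comparison with expert segmentation (10.3) tests agreement and leaves blinding open.

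**3. How much a date shift could matter.** The documents give no figure for this, so the inputs below, apart from the sample size and the test, are assumptions:

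- 20 progressors (10.2), Pearson test at two-sided 0.05 (10.2, 10.3)
- perfusion change standard normal and unrelated to true time to progression
- time to progression uniform over 30 to 210 days (7 months ≈ 210 days)
- poor responder = perfusion change above zero
- in a fraction f of poor responders, the recorded time is max(30, true time − s)

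Results from 100,000 simulated trials per row:

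| Shift s | Fraction f of poor responders | Mean r | Type I error |
|---|---|---|---|
| none | – | 0.00 | 5% |
| 30 days | one quarter | −0.05 | 5–6% |
| 30 days | half | −0.10 | 7% |
| 60 days | one quarter | −0.09 | 7% |
| 60 days | half | −0.19 | 12% |

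The negative sign is the direction of the hypothesis: less fall in perfusion goes with earlier progression. The floor at day 30 avoids impossible negative times. Without it the last row becomes 14%. A 60-day shift is about one clinical scan interval. If only 10% of poor responders are shifted by 60 days, the error stays at about 5%.

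The simulation covers only the route that advances recorded progression. It does not model treatment changes.

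**The case against.** The strongest case on the other side is that this is an openly stated choice in a small single-centre imaging study, and that the text does not show ASL being used. Section 7.4 says available, not reported or acted on. Quantified values need segmentation (10.3) with no stated turnaround, so T1 and T2 values may not reach the clinic before progression is called. RECIST is size-based with numeric thresholds, and ASL has no formal part in it. Routine imaging every 2 to 3 months limits discretion over timing. The phrase in section 5.4 about progression being clinically indicated may only mark the end of the research MRI series. All of this stands. It makes the influence possible rather than demonstrated, and the link to the treating clinics is an inference from the words on clinical RECIST.

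A reader might also infer more than the documents support:

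- **That the bias must favour the hypothesis.** This fits reading and timing effects. A treatment change after a poor ASL result could delay progression and weaken the association.
- **That nothing can be done later.** A later ASL-blind re-read of stored conventional MRI could address reading bias. It could not undo changes in scan timing or treatment.
- **That the type I error is grossly inflated.** Shifting every poor responder by 60 days gives about 39%, but nothing in the documents supports so complete an effect.
- **That ASL must be withheld from clinics.** This reverses an explicit disclosure choice. Withholding ASL alone would also be incomplete, because section 5.4 gives contrast at T0 to T2 to measure the same tumour blood flow.

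**Conclusion.** The point holds as a gap in blinding. If section 7.4 is followed as written, the early perfusion result can influence the reading and timing of the endpoint it is meant to predict, and nothing elsewhere prevents this. Direction is partly known: reading and timing effects would tend to inflate the association, while treatment effects could go either way. Size is unknown. Under the stated assumptions, type I error rises from 5% to about 7% to 12% when progression is recorded 30 to 60 days early in half of the poor responders, and hardly moves when few patients are affected. This calls for a change because the remedy is cheap and works best before reading begins. It does not invalidate the design or the power statement.

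**What to change.** Amend sections 7.4, 6.1 and 10.3 as follows:

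1. The existing reader selects target lesions and records RECIST status at each assessment from conventional images, without access to ASL or research perfusion maps and values.
2. ASL segmentation and perfusion values are locked before linkage to progression data, and those who segment do not see outcome.
3. The CRF records whether research perfusion results were seen or acted on before progression was recorded.
4. A sensitivity analysis repeats the primary correlation without the patients in item 3. It should be read beside the main result, since those patients may mostly be poor responders and their removal narrows the perfusion range.

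As an option, the sponsor may consider delaying release of quantified research perfusion results, both ASL and research contrast perfusion, until the 7-month status or earlier progression is recorded, with conventional images and incidental findings still released. This would also limit the timing and treatment routes, which reader blinding alone does not reach.

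The cost is minor workflow separation and one extra CRF item, with no additional reader. The optional step also means that clinics would not see a developmental measure in real time.
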